Research samples	Deep immunophenotyping Group ⁷			х	Х	х	х	х		х
	Serology Group ⁸			х		x ⁹	х			
Data collec	tion			Х			х		х	х

Key

Page vii v6.0, 14-Jul-2021

¹ Optional sample. Baseline research samples may also be collected prior to recruitment to OCTAVE as part of another Research Ethics Committee (REC) approved study

²Optional sample. To include 3ml tempus sample and 2-3 x 9ml EDTA samples only

³+/- 3 days for the Deep Immunophenotyping Group and -7/+ 56 days for the Serology Group

⁴ Six months after booster, as close to time point as possible

⁵ Six months after booster, data collected retrospectively from participants medical records

⁶Twelve months after first vaccine dose or prior third vaccine dose (if applicable), whichever is earlier

⁷Research samples include: whole blood, peripheral blood mononuclear cells (PBMC), serum, plasma and saliva

⁸ Research samples include: serum as a minimum, whole blood, peripheral blood mononuclear cells (PBMC), and plasma where possible

⁹ Optional sample. Any time after first vaccination but before booster

TABLE OF CONTENTS

1.	BACKGROUND AND RATIONALE	
1.1	SARS-CoV-2 Vaccines	1
1.1.1		
2.	AIM, OBJECTIVES AND OUTCOME MEASURES	
2.1	Objectives	
2.1.1		
2.1.2		
2.2	Outcome Measures	
2.2.1	,	
2.2.2		
2.2.3	, , , , , , , , , , , , , , , , , , , ,	
3.	TRIAL DESIGN	
4. 4.1	ELIGIBILITY Inclusion Criteria	
5. 5.1	SCREENING AND CONSENT	
5.2	Informed Consent	
6.	TRIAL ENTRY	
7.	TRIAL REQUIREMENTS	
7.1	Investigational Medicinal Products	
7.1.1	_	
7.2	Vaccination	
7.2.1	1 First Vaccination	14
7.2.2	Second Vaccination (Booster)	14
7.3	Assessments	14
7.4	Sample Collection and Analysis	14
7.4.1	1 Collection	14
7.4.2	2 Analysis	17
7.4.3	3 Future Research and Biobanking	17
7.5	Participant Follow-Up	17
7.6	Data Linkage	18
7.7	Participant Withdrawal	18
8.	ADVERSE EVENT REPORTING	18
8.1	Reporting Requirements	
8.1.1		
8.1.2	2 Serious Adverse Events	18
8.2	Reporting Period	
8.3	Reporting Procedure	
8.3.1		
8.3.2		
8.3.3		
9.	DATA COLLECTION	
9.1	Archiving	
10.	QUALITY MANAGEMENT	
10.1	Site Set-up and Initiation	
10.2	On-site Monitoring	23

10.3	Central Monitoring 23					
10.4	Audit and Inspection					
10.5	Notification of Serious Breaches	24				
11.	END OF TRIAL DEFINITION	24				
12.	STATISTICAL CONSIDERATIONS	24				
12.1	Definition of Outcome Measures	24				
12.1	.1 Primary Outcome Measures	24				
12.1	.2 Secondary Outcome Measures	24				
12.2	Analysis of Outcome Measures	25				
12.2	.1 Primary Outcome Measures	25				

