2.2.3.2 Cellular Immunogenicity

- The relative contribution of T cell subsets and T cell function will be assessed using intracellular cytokine analysis and flow cytometry (ICCS) established at Oxford University laboratories (https://www.biorxiv.org/content/10.1101/2020.06.05.134551v1)
- Proliferation assays (CTV assay)) will evaluate the recall potential of SARS-CoV-2 memory T cells at later (6 month) time points (established at Oxford University laboratories https://www.biorxiv.org/content/10.1101/2020.06.05.134551v1)

Additional assays relevant to immune state and response may be undertaken:

- Serum antibodies (IgG/IgM/IgA) to important SARS-CoV-2 antigens and SARS-CoV-2 related antigens (including but not limited to SARS, MERS and circulating seasonal coronaviruses: CoV-2 S, NL63 S, CoV-2 N, CoV-1 S, MERS S, HKU1 S, OC43 S, 229E S, CoV-2 RBD) will be measured in an MSD assay or bespoke ELISA established at University of Glasgow laboratories
- Saliva antibodies (IgG/IgA) to both the spike (S) and the nucleocapsid (N) antigens of SARS-CoV-2 will be measured using an optimised saliva ELISA developed by the University of Bristol
- Flow cytometric characterisation of the circulating immune compartment (e.g. T cells and B cells) will be undertaken
- T cell and B cell specific responses to defined peptides/stimuli will be undertaken using established ELISpot assays, at Imperial College London and Oxford University laboratories

Furthermore, other assays may be added as data emerges from OCTAVE and other related studies.

OCTAVE will include an optional additional blood sample 1-day post-vaccine that can be requested from trial participants primarily for next generation sequencing approaches (e.g., RNA sequencing) to evaluate in detail early innate responses at this time point.

Page 8 of 40 v6.0, 14-Jul-2021

TRIAL DESIGN

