 Previously treated with autologous or allo-HSCT for any indication and with any conditioning regimens and intensities

Previously treated with CAR-T cell therapies

Note: HSCT and CAR-T recipients who have received one or two doses of a SARS-CoV-2 vaccine pre-procedure and are receiving re-vaccination post HSCT / CART-T are eligible for recruitment at:-

- Baseline (prior to re-vaccination dose 1) to either Deep Immunophenotyping Group or Serology Group
- For the Deep Immunophenotyping Group, before they received the second revaccination dose
- For the Serology Group, up to 28 (-7 /+ 56) days post second re-vaccination only if 2 doses have been administered post-HSCT / CAR-T procedure.

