6.4 Sample Collection and Analysis

6.4.1 Collection

Sites will be provided with kits for the collection of the research samples.

For the **Deep Immunophenotyping Group** up to 55ml of blood will be collected from participants at any one visit comprising whole blood, peripheral blood mononuclear cells (PBMC), serum and plasma. Saliva samples will also be collected. Samples will be collected at the following time points:

- Pre-vaccine (baseline) this is an optional time point, samples may have been collected prior to recruitment to OCTAVE
- 1 day after first vaccination this is an optional time point*
- Pre-booster
- 28 days post-booster (within +/- 3 days)
- 6 months post booster (as close to time point as possible)
- 12 months after first vaccine dose or prior to third vaccine dose (if applicable), whichever earlier**
- * 3ml Tempus sample and 2-3 x 9ml EDTA samples required at this time point
- ** 2 x 5ml SST samples required at this time point

CRCTU-PRT-QCD-001, version 1.0

Page 14 of 40 v6.0, 14-Jul-2021

For the **Serology Group** as a minimum 10ml of serum will be collected, but where possible whole blood, PBMC, and plasma will also be collected, from participants at the following time points:

- Pre-vaccine (baseline) this is an optional time point, samples may have been collected prior to recruitment to OCTAVE
- Pre-booster this is an optional time point, any time after the first vaccination but before booster
- 28 days post-booster (-7/+56 days)

See Table 1 for further details on samples types collected and storage conditions.

Full details of the sample collection and processing procedure are included in the Laboratory Manual.

Table 1: Details of Sample Collection and Storage

Sample Type	Collection Tube	Volume	Laboratory Analysis	Aliquots	Sample Storage
Whole Blood	Tempus	3ml	RNA	None	-80°C
	RNA				
Whole Blood	EDTA	9ml x	Cellular	4 x 500ul (as	-80°C for
		minimum of	immunoassays	PBMCs)	Plasma (long-
		2 (maximum	& DNA	5 x 700ul (as	term) and
		of 3)		Plasma)	PBMCs (short-
					term), then
					liquid nitrogen
					or -150 °C;
					depends on site
					(long-term)
Serum	SST	5ml x 2	Immunoassay;	10 x 400ul	-80°C
			ELISA and virus		
			neutralisation		
			assays		
Whole Blood	Lithium	6ml x 2	ELISpot assay	None	None
	Heparin*				
Saliva [†]	Saliva	1 spit up to	Immunoassay	1	-80°C
	collection	1ml mark on			
	funnel and	collection			
	10ml	tube			
	collection				
	tube				

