6.4.2.2 Serology Group

Laboratory analysis to be conducted on the Serology Group samples are expected to include:

- Assessment of quantitative IgG responses to SARS-CoV-2 spike and nucleocapsid antigens will be undertaken by the Public Health England Laboratories at Porton Down
- Assessment of neutralising antibody responses to SARS-CoV-2 antigens be undertaken at both the laboratories at the University of Glasgow and the Public Health England Laboratories at Porton Down
- Assessment of IgG/IgM/IgA responses to SARS-CoV-2 antigens and other relevant season antigens will be undertaken by the laboratories at the University of Glasgow
- Assessment of IgG/IgA responses to SARS-CoV-2 spike and nucleocapsid antigens will be undertaken by laboratories at the University of Bristol

This is not an all-inclusive list, additional assays will be included as more information becomes available about the immune response.

Principal Investigators will be provided with the results of their patients' assessment of immune response. Participants should be provided with the results on request.

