6.5 Participant Follow-Up

Participants will be followed up in accordance with standard clinical practice for the relevant disease cohort.

Data will be collected retrospectively from clinic records 6 months after the second vaccination and 12 months after first vaccination or at the time or 3rd vaccination (whichever is earlier). Data collected from face-to-face consultations or telephone follow-up calls are acceptable.

Page 17 of 40 v6.0, 14-Jul-2021

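### Deep Immunophenotyping Group: only the 12-month sample must precede a third dose, so the 6-month sample can be a three-dose sample; dose counting for re-vaccinated HSCT/CAR-T recipients is not carried into the schedule

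*Protocol*

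**What the plan says.** **Late samples.** Section 6.4.1 gives the Deep Immunophenotyping Group two late samples. The first is "6 months post booster (as close to time point as possible". The second is "12 months after first vaccine dose or prior to third vaccine dose (if applicable), whichever earlier". The Trial Synopsis makes the same distinction. So does the Schedule of Events, where footnote 4 reads "Six months after booster, as close to time point as possible" and only footnote 6 mentions a third dose. The Serology Group has neither sample.

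**Tubes and assays.** For the 12-month sample, section 6.4.1 adds "2 x 5ml SST samples required at this time point". Table 1 assigns lithium heparin tubes to the ELISpot assay, EDTA tubes to cellular immunoassays, and SST tubes to serum work. Section 2.2.3.2 says that proliferation assays "will evaluate the recall potential of SARS-CoV-2 memory T cells at later (6 month) time points".

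**Follow-up data.** Section 6.5 collects clinical data 6 months after the second vaccination, without a third-dose limit, and "12 months after first vaccination or at the time or 3rd vaccination (whichever is earlier".

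**Analysis and data capture.** Section 10.2.1 plans mixed models giving slopes and time-point estimates, plus two-sample t-tests of IgG at specific time points. It mentions no third dose. In Table 2 the vaccination forms cover the first and second doses. A third vaccination appears only as a trigger for the Follow-up form, and its date is not among the listed contents.

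**Re-vaccinated recipients.** The note in section 3.1 admits "HSCT and CAR-T recipients who have received one or two doses of a SARS-CoV-2 vaccine pre-procedure" who are then re-vaccinated. It places their baseline before re-vaccination dose 1, Deep Immunophenotyping entry before re-vaccination dose 2, and Serology entry up to 28 (-7/+56) days after re-vaccination dose 2. Section 2.2.2.1 counts COVID-19 from 14 days after the first vaccine dose.

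**The concern.** The protocol foresees third doses within 12 months of the first and moves one late sample ahead of them, but not the other. The trial does not control when doses are given, so a third dose can precede the 6-month visit. The sample labelled 6 months post-booster is then a three-dose measurement, and the visit order reverses.

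Section 1.1 says that durability will be assessed, and T cell response is one of the two primary outcomes. If samples are analysed by visit label alone, a 6-month mean that includes three-dose samples would sit too high as an estimate of two-dose persistence. Recording the third-dose date lets an analyst separate these samples. Nothing in the analysis can replace a late two-dose cellular sample that was never drawn.

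The second issue is one of definition. Entry for re-vaccinated HSCT/CAR-T recipients is tied to re-vaccination doses, but the clocks that run after entry use dose names that do not say which course they count.

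**Working it through.** The protocol states no third-dose date, no proportion affected and no sample-size calculation (section 10.2.5), so there is no figure of its own to reproduce. The dose timings, shares and fold rises below are assumptions.

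**1. When does the 6-month sample become a three-dose sample?** Count weeks from dose 1. Let D be the interval from dose 1 to dose 2 and T the week of dose 3.

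- 6-month sample: week D + 26
- 12-month sample: no later than week min(52, T)
- Three-dose 6-month sample if T < D + 26, that is, if dose 3 comes less than 26 weeks after dose 2

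| D (assumed) | T (assumed) | 12-month sample by week | 6-month sample at week | Result |
|---|---|---|---|---|
| 12 | 36 | 36 (24 after dose 2) | 38 | three-dose, order reversed |
| 8 | 30 | 30 (22 after dose 2) | 34 | three-dose, order reversed |
| 3 | 30 | 30 (27 after dose 2) | 29 | both two-dose |
| 12 | 40 | 40 (28 after dose 2) | 38 | both two-dose |

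If the 6-month sample carried the same condition, it would fall at min(D + 26, T). No sample would then be taken after dose 3, whatever D and T are.

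**2. How far could the 6-month mean move?** Let a share f be sampled after dose 3, with an F-fold rise over the two-dose value they would otherwise have had. The mean log response moves by f × log F, so the geometric mean is multiplied by F^f.

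| f | F = 10^0.5 (about 3.16) | F = 10 |
|---|---|---|
| 0.05 | 1.06 | 1.12 |
| 0.10 | 1.12 | 1.26 |
| 0.25 | 1.33 | 1.78 |
| 0.50 | 1.78 | 3.16 |

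At f = 0 the factor is 1. A more extreme pair, f = 0.5 and F = 30, gives 30^0.5 = 5.5.

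**3. Which assays keep a late two-dose sample?** With an early third dose, the last sample before it is the 12-month one.

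- Antibody assays use SST serum, which that visit lists, so a two-dose value exists, though earlier than intended.
- ELISpot needs lithium heparin and the cellular assays need EDTA. The section 6.4.1 note lists neither for that visit.
- The Synopsis and Schedule of Events footnote 7 describe the full sample set without this restriction, so the tube lists do not agree clearly.

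**4. How do doses count for re-vaccinated recipients, read literally?** R1 and R2 are the first and second re-vaccination doses.

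| Pre-procedure doses | R1 is dose | R2 is dose | Latest time for the last sample |
|---|---|---|---|
| 1 | 2 (the booster) | 3 | before R2 |
| 2 | 3 | 4 | before R1 |

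With two earlier doses, the last sample falls at or before the baseline that section 3.1 defines, and the 12-month data collection is due at R1. The COVID-19 clock starts before the procedure. With one earlier dose, R1 is the booster, so the sample 28 days post-booster follows R1 and not R2.

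**The case against.** **Analysis rules belong in the SAP.** Section 10.2 defers full details to the SAP, which was not among the documents seen. Classifying samples by dose and using actual days are matters for it, and section 10.2.1 already allows flexible longitudinal models. This stands for the analysis rules. It does not cover the sampling condition, the tube list or the CRF contents, which the protocol fixes.

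**Serum is largely protected.** This also stands. A participant with an early third dose still gives a two-dose serum sample just before it. The unprotected part is cellular, and the recall assay at 6 months is exploratory.

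**The problem may not arise.** The protocol mentions a third dose only as a possibility. If none comes within 26 weeks of dose 2, nothing mixes. This is why no size can be fixed.

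A reader might infer more than the text supports:

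- *That the 12-month sample also mixes two- and three-dose responses.* In participants vaccinated in the ordinary way it precedes any third dose by rule. What varies is time since dose 2: with assumed intervals of 12 and 3 weeks, 365 − 84 = 281 to 365 − 21 = 344 days, and less if a third dose brings the sample forward.
- *That re-vaccinated recipients are not re-indexed at all.* Section 3.1 re-indexes their entry and baseline. The intended counting is probably by re-vaccination dose; it is simply not carried into the later clocks.
- *That third-dose timing follows the measured response.* Section 6.4.2.2 says "Principal Investigators will be provided with the results of their" patients' assessments. That sentence stands under the Serology Group, and no text links results to third-dose timing.
- *That the most immunosuppressed receive a third dose earliest.* This is plausible but undocumented.

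**Conclusion.** The point holds within limits. In the Deep Immunophenotyping Group the 6-month sample lacks the pre-third-dose condition given to the 12-month sample. Anyone whose third dose comes less than 26 weeks after the second gives a mislabelled 6-month sample, out of order. Antibody measurement keeps a two-dose fallback; the T cell assays, including the 6-month recall assay, have none assured.

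The size cannot be determined from the protocol. The factors in the working, from 1 up to 5.5, depend entirely on the assumed share and boost, and apply only if samples are analysed by visit label with no dose rule. The documents do not support saying that waning will be understated; they support saying that it could be.

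The HSCT/CAR-T issue is a gap between section 3.1 and the Schedule of Events and sections 2.2.2.1, 6.4.1 and 6.5. The literal result, a last sample no later than baseline, is unlikely to be intended, which is a reason to state the counting. Both matters should be corrected; neither undermines the design.

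**What to change.** 1. **Data capture.** Add the third-dose date to the Follow-up form. Section 9 allows CRF changes without a protocol amendment.
2. **Analysis.** In section 10.2 or the SAP, classify each sample by the doses received at its collection date. Keep samples taken after a third dose out of two-dose estimates and report them separately. Model pre-third-dose samples by actual days since dose 2 rather than by visit label.
3. **Sampling.** Reconcile the 6- and 12-month conditions in the Synopsis, Schedule of Events and section 6.4.1. Reconcile the tube lists too, so that it is clear whether a pre-third-dose visit supplies cellular material.
4. **Dose counting.** State in the Schedule of Events and sections 2.2.2.1, 6.4.1 and 6.5 how first, second and third doses are counted for the re-vaccinated recipients in section 3.1, consistently with their re-indexed entry.

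The cost is one CRF field, an analysis rule, a short dose-counting statement and a wording reconciliation. The main downside is fewer two-dose samples at 6 months. If cellular tubes are added to the pre-third-dose visit, those participants also give more blood and the laboratories process more samples.

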6.4.2 Analysis

6.4.2.1 Deep Immunophenotyping Group

Laboratory analysis to be conducted on the Deep Immunophenotyping Group samples will include:

- Assessment of IFN-g T cell responses to SARS-CoV-2 antigens in an ex vivo ELISpot assay, to be undertaken by Oxford Immunotec
- Assessment of fine specificity of T cell and B cell responses (ELISpot and Flow cytometric) will be performed by laboratories at the University of Oxford and Imperial College London

This is not an all-inclusive list; additional assays will be included as more information becomes available about the immune response.

6.4.2.2 Serology Group

Laboratory analysis to be conducted on the Serology Group samples are expected to include:

- Assessment of quantitative IgG responses to SARS-CoV-2 spike and nucleocapsid antigens will be undertaken by the Public Health England Laboratories at Porton Down
- Assessment of neutralising antibody responses to SARS-CoV-2 antigens be undertaken at both the laboratories at the University of Glasgow and the Public Health England Laboratories at Porton Down
- Assessment of IgG/IgM/IgA responses to SARS-CoV-2 antigens and other relevant season antigens will be undertaken by the laboratories at the University of Glasgow
- Assessment of IgG/IgA responses to SARS-CoV-2 spike and nucleocapsid antigens will be undertaken by laboratories at the University of Bristol

This is not an all-inclusive list, additional assays will be included as more information becomes available about the immune response.

Principal Investigators will be provided with the results of their patients' assessment of immune response. Participants should be provided with the results on request.

6.4.3 Future Research and Biobanking

Any samples remaining at the end of the trial will be banked in a Human Tissue Authority (HTA) licenced biobank. The samples and data will be made available for future research in other ethically approved studies (see Section 13.3 and Section 18 for further details).

6.5 Participant Follow-Up

Participants will be followed up in accordance with standard clinical practice for the relevant disease cohort.

Data will be collected retrospectively from clinic records 6 months after the second vaccination and 12 months after first vaccination or at the time or 3rd vaccination (whichever is earlier). Data collected from face-to-face consultations or telephone follow-up calls are acceptable.

Page 17 of 40 v6.0, 14-Jul-2021

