1.1.1.3 Chronic Renal Diseases

End-stage kidney disease (ESKD) is one of the strongest risk factors for severe COVID-19 (estimated hazard ratio for death 3.69) [33], and ESKD patients hospitalised with COVID-19 have a mortality of approximately 30% [34-37]. The UK renal registry and NHS Blood and Transplant have reported UK

Page 5 of 40 v6.0, 14-Jul-2021

national mortality rates of 19% in haemodialysis (HD) patients, and over 25% in renal transplant patients with COVID-19 [28, 38].

ESKD patients have a high prevalence of vascular and cardiometabolic disease (e.g. hypertension, ischaemic heart disease, diabetes), either as a result of the underlying cause of their renal disease and/or as a consequence of renal failure. In addition, ESKD results in both relative immunosuppression and chronic low-grade inflammation [39-44], which may impact viral defence and the host inflammatory response. As well as being enriched for cardio-metabolic risk factors, the ESKD group being studied at Imperial College NHS Trust also has a high proportion of Black, Asian, Minority Ethnic (BAME) origin patients. Of the patients sampled in this on-going study, 72% are non-white, including 17% of African or Afro-Caribbean origin and 42% of South Asian origin. Patients in these subgroups are at higher risk of death from COVID-19 pneumonia.

Poor seroconversion is well-documented following standard vaccinations amongst haemodialysis patients [33] and we have observed a high rate of recurrent SARS-CoV-2 infection in haemodialysis (HD) patients. Current medications have not improved SARS-CoV-2 -related mortality in these cohorts [38], and HD patients cannot easily socially distance when required to attend dialysis units several times per week [45].

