2.2.2 Secondary Outcome

2.2.2.1 Clinical protection

First symptomatic, PCR-proven COVID-19 occurrence from 14 days after first dose of SARS-CoV-2 vaccine in participants without evidence of prior infection with SARS-CoV-2

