6.6 Data Linkage

The participant's NHS number or CHI number will be collected to allow future linkage with national data registries such as NHS Digital, Public Health England, the Information Services Division (part of NHS Scotland), or the electronic Data Research and Innovation Service (eDRIS). For the HSCT participant group the British Society of Blood and Marrow Transplantation (BSBMT) registry identification (PROMISE ID) will also be collected, where participants have also consented to collection of data within this registry, to allow for data linkage. Data linkage will provide a more complete profile of the participants' health and disease without increased data collection burden to the NHS.

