9. DATA COLLECTION

The CRF will be comprised of the forms listed in Table 2.

Page 20 of 40 v6.0, 14-Jul-2021

Table 2: OCTAVE Trial Case Report Form

	Form	Summary of Data Recorded*	Schedule for Submission to Trial Office	
Registration		Minimal identifiers (initials and date of birth)	Complete at trial entry	
Baseline		NHS/CHI/ BSBMT registry ID, hospital number, demographic data (sex, ethnicity), World Health Organisation (WHO) performance status (Appendix 3), body mass index, medical history including comorbidities, disease group specific information (including disease status), details of prior COVID-19 infection, collection of baseline research samples	Within 1 month of trial entry	
Treatment Form	First vaccination Second vaccination	Details of rituximab, corticosteroids, and nonsteroidal anti-inflammatory drugs (NSAIDs) and other disease cohort specific	As soon as possible after relevant vaccination	
Vaccination form	First vaccination	treatments Date of vaccination Type of vaccination Batch number (if known) Planned date of booster (if known)	As soon as possible after relevant vaccination	
	Second vaccination	Date of booster Type of vaccination Batch number (if known)		
Vaccination Adverse Reaction	First vaccination	Details of ARs thought to be related to SARS-CoV-2	As soon as possible after relevant vaccination	
Form	Second vaccination	vaccination	relevant vaccination	
Research San	nple Collection Form	Confirmation of collection of research samples in accordance with the protocol	As soon as possible on collection of research samples	
Follow-up		Survival data, COVID-19 infection data, WHO performance status, disease site specific	Six months post second vaccination (booster) and 12 months post first vaccine or third vaccination	

Page 21 of 40 v6.0, 14-Jul-2021

Form	Summary of Data Recorded*	Schedule for Submission
		to Trial Office
Death	Date and cause of death	Immediately upon notification
Death	Date and cause of death	of participant's death
	Used to notify the Trial Office of	Immediately upon patient
Withdrawal of Consent	the participant's withdrawal from	withdrawal
	the trial	Withdrawai
	Details on deviations from the	Immediately upon discovery of
Deviation Form	protocol not captured elsewhere	a deviation
	on the CRF	a deviation
	Details of any SAE thought to be	No later than 24h after
Serious Adverse Event	related to SARS-CoV-2	
	vaccination	becoming aware of the event

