^{*} It is anticipated data will collected retrospectively from the participants medical records.

This trial will use an eRDC system to capture the CRF data, the only exception to this will be the registration data which will be captured in an Excel workbook (a paper version of the Registration Form is also available) and the SAE Form which will be completed on paper.

Access to the eRDC system will be granted to site research staff by the Trial Office.

https://crctu.redcap.bham.ac.uk/

The investigator and site staff will ensure all data is promptly entered into the eRDC system in accordance with the trial specific User Manual and CRF Completion Guidelines. The CRF must be completed by the investigator or an authorised member of the site research team (as delegated on the Site Signature and Delegation Log).

Entries on the paper CRF should be made in ballpoint pen, in blue or black ink, and must be legible. Any errors should be crossed out with a single stroke, the correction inserted and the change initialled and dated. If it is not obvious why a change has been made, an explanation should be written next to the change.

Data reported on the CRF should be consistent with the source data or the discrepancies should be explained. If information is not known, this must be clearly indicated on the form. All missing and ambiguous data will be queried. All sections are to be completed before returning.

In all cases it remains the responsibility of the investigator to ensure that the CRF has been completed correctly and that the data are accurate.

The CRF may be amended from time to time by the Trial Office throughout the duration of the trial. Whilst this will not constitute a protocol amendment, new versions of the CRF must be implemented by participating sites immediately on receipt.

Page 22 of 40 v6.0, 14-Jul-2021

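### The only secondary outcome, symptomatic PCR-proven COVID-19, is read from records of cohort-specific usual care, so event capture can differ by cohort; linked PCR results should be the named source

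*Protocol*

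**What the plan says.** Section 2.2.2.1 defines the one secondary outcome: "First symptomatic, PCR-proven COVID-19 occurrence from 14 days after first dose of SARS-CoV-2 vaccine", in participants with no evidence of earlier infection.

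Section 6.5 sets how events reach the trial. On the intensity of contact it says: "Participants will be followed up in accordance with standard clinical practice for the relevant disease cohort". On the source of the data and the two extraction dates it says: "Data will be collected retrospectively from clinic records 6 months after the second vaccination and 12 months after first vaccination"; the later date is brought forward if a third dose comes sooner. On other forms of contact it says: "Data collected from face-to-face consultations or telephone follow-up calls are acceptable", so calls are permitted but not required.

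In Table 2 (Data Collection), the Follow-up form carries the event: "Survival data, COVID-19 infection data, WHO performance status, disease site specific". The footnote to that table reads "It is anticipated data will collected retrospectively from the participants medical records".

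Section 6.6 says that the NHS or CHI number is collected "to allow future linkage with national data registries such as NHS Digital, Public Health England" and other bodies. It does not connect linkage to the COVID-19 outcome.

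Section 10.2.2 provides Kaplan-Meier and Cox methods for time-to-event data, where appropriate. Section 10.2 states that the primary and secondary outcomes are assessed by methods that permit participants to be compared directly and that eliminate bias from measurement.

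**The concern.** An infection counts only if it reaches a record that the site reads. How readily that happens depends on how often the participant is in contact with the service, and contact is set by disease cohort. Cohort is also the natural comparison variable in this study.

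The protocol gives one contact frequency. Section 1.1.1.3 says that haemodialysis patients are "required to attend dialysis units several times per week". No frequency is given for any other cohort.

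If capture differs by cohort, the difference cannot be separated from the cohort effect, and covariate adjustment in a Cox model does not remove it. A cohort with fuller records would look less protected, and one with thinner records better protected, at the same true incidence. The claim in 10.2 is credible for a central laboratory assay. It has no basis for an event read retrospectively from records that each specialty generates in its own way.

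**Working it through.** **No figure to reproduce.** The protocol states no event rate, capture rate, power or alpha for this outcome, and 10.2.5 says that no formal sample size calculation was feasible. What follows is an illustration.

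**Inputs from the protocol.** Section 10.2 gives 100 to 200 participants per disease cohort in the Deep Immunophenotyping Group and 150 to 850 in the Serology Group. A cohort contributing to both therefore has 100 + 150 = 250 to 200 + 850 = 1,050 participants. The numbers at risk would be smaller, because participants with prior infection are excluded.

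**Assumptions, not in the protocol.** Equal true cumulative incidence p of 5% or 10% in two cohorts; capture c1 = 95% in one and c2 = 80%, 65% or 50% in the other; equal cohort sizes n; two-sided alpha 0.05; n = 500 as a middle value.

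**Apparent hazard ratio.** Observed cumulative incidence is p × c. The apparent hazard ratio, better-captured against less-captured cohort, is ln(1 − p·c1) / ln(1 − p·c2), which for rare events is close to c1/c2.

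| Capture | c1/c2 | p = 5% | p = 10% |
|---|---|---|---|
| 95% v 95% | 1.00 | 1.00 | 1.00 |
| 95% v 80% | 1.19 | 1.19 | 1.20 |
| 95% v 65% | 1.46 | 1.47 | 1.49 |
| 95% v 50% | 1.90 | 1.92 | 1.95 |

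The true hazard ratio is 1 throughout. Cohort size does not enter the formula, so recruiting more participants leaves the bias unchanged.

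**Chance of a false finding.** Expected captured events are D = n·p·(c1 + c2). By Schoenfeld's formula, the chance of a significant result in the direction of the bias is Φ(√D·|ln HR|/2 − 1.96); without bias it would be 2.5% in that direction. For n = 250, p = 5% and 95% v 80%: D = 250 × 0.05 × 1.75 = 21.9, |ln HR| = 0.176, and Φ(0.41 − 1.96) = 6.1%.

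| n per cohort | p | v 80% | v 65% | v 50% |
|---|---|---|---|---|
| 250 | 5% | 6.1% | 13.7% | 28.5% |
| 250 | 10% | 8.6% | 23.9% | 51.8% |
| 500 | 5% | 8.4% | 23.1% | 50.3% |
| 500 | 10% | 13.2% | 42.4% | 80.9% |
| 1,050 | 5% | 13.2% | 42.6% | 81.3% |
| 1,050 | 10% | 23.0% | 72.7% | 98.4% |

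The estimate stays biased at every size, and a larger cohort only makes the false difference more likely to be declared significant.

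**The case against.** The case on the other side has real content.

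- **A reader might infer that the protocol prespecifies a disease-to-disease Cox comparison of COVID-19.** It does not. In 10.2.2 the disease-to-disease and disease-to-control wording belongs to response estimates compared by t-test; the Kaplan-Meier and Cox sentence names no groups. The objectives concern immune response. The comparison is implied by the choice of a Cox model and by the direct-comparison claim in 10.2.
- **A reader might infer that contact frequency is known to differ greatly between cohorts.** Only haemodialysis has a stated frequency, and the renal cohort also includes transplant recipients. The text supports *can differ* and no more.
- **Capture may be better than clinic visits alone suggest.** The Table 2 footnote refers to medical records, telephone calls are accepted, every cohort completes the same Follow-up form, and missing data are queried. This stands, but none of it requires anyone to ask the participant, and a query cannot recover an infection that no record mentions.
- **A reader might infer that linkage would give a uniform source.** It would not. Several bodies are listed, with separate ones for Scotland; nothing shows that they hold symptom status; and linkage equalises neither how often cohorts are tested nor their exposure. Section 1.1.1.3 itself notes that haemodialysis patients cannot easily distance.
- **Hospitalisation or death might seem a cleaner alternative.** The protocol gives no ground for saying that these are recorded more evenly.
- **The statistical analysis plan, not shown, may set rules for combining sources.** It may, but the collection source is fixed in the protocol, and an analysis plan cannot recover events that were never captured.

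**Conclusion.** The point holds in a limited form. Ascertainment of the only secondary outcome depends on cohort-specific usual care, and the statement in 10.2 about comparability and measurement bias is not justified for it. A between-cohort hazard ratio would be distorted by about the ratio of capture probabilities: roughly 1.19 to 1.20 for 95% v 80%, rising to 1.92 to 1.95 for 95% v 50%. The size in this trial is unknown, because capture and incidence are assumptions throughout. At the mildest contrast and the smallest cohorts, the risk of a false significant result is modest (6.1% to 8.6% against 2.5%), though the estimate is still biased. The primary immunogenicity outcomes are not touched. The change is worth making because the identifiers are already collected, linkage is already foreseen, and the trial stays open for 18 months after the last data capture.

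**What to change.** 1. In 2.2.2.1 and 6.6, name linked national PCR results, obtained through the NHS/CHI number, as the primary source for occurrence and date of PCR-proven infection in every cohort. Use clinic or medical records to confirm symptoms, and report agreement between the two sources by cohort.
2. Add a sensitivity analysis on PCR-proven infection regardless of symptoms, because symptom status may still be captured unequally.
3. Until linkage is available, report COVID-19 incidence by cohort descriptively, without between-cohort hazard ratios.
4. In 10.2, restrict the statement on direct comparison and measurement bias to the laboratory assays.

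The cost is a linkage application and some delay to this outcome; no extra visits are needed. Linkage makes capture more uniform but leaves differences in testing frequency and exposure, and the report should say so.
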